4.4.3 Secondary Endpoints of Dose-Escalation and Dose-Expansion Phases

4.4.3.1 Safety

- Nature, incidence and severity of AEs measured from baseline to end of trial participation

NOTE: Adverse Events are graded by the Investigator according to the National Cancer Institute-Common Terminology Criteria for Adverse Events (NCI-CTCAE v.4.03, in the following referred to as CTCAE)

- AEs leading to dose-reductions, dose delays and permanent treatment cessation
- Changes in safety laboratory values from baseline to end of trial participation
- Changes in vital signs and physical examinations from baseline to end of trial participation
- Occurrence of anti-drug antibodies (ADA) to Sym004 measured in serum at selected timepoints from baseline to end of trial participation

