7.1.4.2 Dose-Escalation Phase

During the dose-escalation phase of the trial, the following dose levels of Sym004 will potentially be evaluated in combination with FOLFIRI:

- Dose Level 1: Sym004 12 mg/kg + FOLFIRI
- Dose Level 2: Sym004 15 mg/kg + FOLFIRI
- Dose Level 3: Sym004 18 mg/kg + FOLFIRI

If the toxicity profile of Dose Level 1 indicates that this dose is not tolerated, successive lower dose levels will be explored:

- Dose Level -1: Sym004 9 mg/kg + FOLFIRI
- Dose Level -2: Sym004 9 mg/kg (loading dose) + FOLFIRI followed by 6 mg/kg + FOLFIRI
- Dose Level -3: Sym004 6 mg/kg + FOLFIRI

If Sym004 at 9 mg/kg + FOLFIRI (Dose-Level -1) has not exceeded the MTD and is well tolerated during Cycle 1, but overall tolerability is judged to be insufficient to accept this dose level as the RP2D, then Dose Level -2 may be explored.

If Sym004 at 9 mg/kg + FOLFIRI (Dose-Level -1) during Cycle 1 has not exceeded the MTD, but tolerability is judged to be insufficient to accept this dose level as the RP2D, then Dose-Level -3 may be explored.

If the toxicity profile of lower doses where mandatory diarrhea prophylaxis is utilized indicates that the dose is well tolerated, further evaluation of Dose Level 1, and potentially Dose Levels 2 and 3 may take place after approval by the ISMC.

Cohorts will be filled sequentially. Patients will be allocated to the next available treatment slot within the current or next cohort, as appropriate and depending on the ongoing observation of DLTs and other safety parameters.

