9.5.2 Observation Period for Dose-Limiting Toxicities

Throughout the dose-escalation phase, the decision to dose-escalate is based on close monitoring of safety during the observation period for DLTs, defined as Cycle 1, i.e. the initial 28 day period (± 2 days) from first treatment of Sym004 in combination with FOLFIRI.

A minimum of 2 infusions of Sym004 in combination with FOLFIRI (full doses) must have been administered for a patient to have completed and tolerated the DLT observation period.

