10 STATISTICS

10.1 Sample Size Determination

The primary endpoint of the dose-escalation phase is the occurrence of DLTs on each of the Sym004 dose levels given in combination with FOLFIRI. The number of enrolled patients will depend on the extent of observed DLTs independently in each cohort. Please, refer to [Section 7.1.4.2](#) and [7.1.4.3](#) for a description of planned dose levels and decision tree for dose-escalation. Based on a 3 + 3 design, it is planned to enroll between 9 and 18 patients during dose-escalation.

In the dose-expansion phase of the trial, the primary endpoint is confirmed objective antitumor response to the combination of Sym004 and FOLFIRI. The number of patients planned to be included in this part of the trial is 32-41 patients depending on the number of patients enrolled in the dose-escalation phase.

In a Phase III study of patients with CRC treated with a second line regimen including panitumumab plus FOLFIRI, the response rate reported was 35% or 36% ([21](#), [22](#)). In one phase II study of CRC patients treated with cetuximab plus FOLFIRI as a second line regimen, a response rate of 32% was observed ([23](#)). The results from these studies were utilized as references to consider an increment in response rate that would support further studies to evaluate the potential efficacy of the combination of Sym004 and FOLFIRI.

If between 32 and 41 patients are included in the dose-expansion phase of the trial, the lower 90% exact confidence bound of a 47% observed response rate is at least 32%.

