10.3 Primary Endpoint and Analysis

10.3.1 Dose Escalation Phase

The primary objective of the dose-escalation phase is to determine the MTD of Sym004, assessed by the occurrence of DLTs during the DLT observation period for each of the Sym004 dose levels given in combination with FOLFIRI.

All DLT events (if any) will be listed by dose cohort and patient. A summary table of DLTs by System Organ Class (SOC) and preferred term will be presented for each dose cohort, if applicable. The summaries will include number of DLTs and number and percentages of patients who experienced a DLT. The definition of a DLT is included in [Section 9.5.1](#). The MTD is defined as the highest dose with a maximum of 1 out of 6 patients experiencing a DLT. The MTD might not be found.

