10.4.1 Safety Endpoints and Analyses

The safety endpoints are presented below and will all be presented for the FAS by trial phase. Safety data will only be presented descriptively, and no formal statistical analyses will be performed.

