10.4.1.1 Adverse Events

The AEs will be coded using Medical Dictionary for Regulatory Activities (MedDRA) current version. AEs will be regarded as treatment emergent AEs (TEAEs) if they occur after first treatment. Non-treatment emergent AEs (Non-TEAEs) are defined as AEs collected before dosing. TEAEs will be presented by SOC and preferred term unless stated otherwise. The frequencies of TEAEs will be presented including number and percentages of patients having experienced an event and the total number of events.

AEs including SAEs are reported from signing the informed consent until the end of trial participation. SAEs reported outside the required reporting window are only entered into the safety database and will be described separately in the report.

NOTE: Patients who sign the informed consent and are subsequently deemed to be screening failures will be followed for the occurrence of SAEs/AEs until it is determined they will not be participating in the trial.

All AEs will be listed. The TEAEs will be presented using summary tables by trial phase including:

- AEs, in total and sorted by frequency
- AEs by relationship
- AEs by CTCAE Grade and max CTCAE Grade
- Skin toxicity AEs defined as AEs within a predefined set of preferred terms (list to be included in the Statistical Analysis Plan [SAP])
- AEs of Medical Interest
- SAEs, in total, and by relationship
- AEs leading to withdrawal from treatment
- AEs leading to trial drug interruption or dose reduced
- Fatal AEs

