10.4.1.2 Clinical Laboratory Values

Biochemistry, hematology and coagulation parameters will be presented using box plots by visits and by cohort and trial phase. In addition, individual patient biochemistry, hematology and coagulation parameters during the trial will be presented graphically using longitudinal plots. Urinalysis parameters will be summarized using descriptive statistics.

Laboratory values outside normal range by flagged and all laboratory values will be listed including CTCAE grading of abnormal values.

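### The TEAE tables are split by trial phase only, so escalation-phase adverse-event frequencies and grades are pooled over different Sym004 dose levels

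*Protocol*

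**What the plan says.** Section 10.4.1 of the protocol gives the general rule that the safety endpoints "will all be presented for the FAS by trial phase". Section 10.4.1.1 repeats it for adverse events: "The TEAEs will be presented using summary tables by trial phase including" overall frequency, relationship, CTCAE grade and maximum grade, skin toxicity, SAEs, AEs leading to withdrawal, AEs leading to interruption or dose reduction, and fatal AEs. Neither section names dose cohort for these tables.

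Section 7.1.4.2 says that in the escalation phase "the following dose levels of Sym004 will potentially be evaluated in combination with FOLFIRI" and lists six levels, from 6 to 18 mg/kg. Section 5.1 speaks of up to five. Section 10.1 states that "it is planned to enroll between 9 and 18 patients during dose-escalation".

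The safety endpoints in section 4.4.3.1 include "Nature, incidence and severity of AEs measured from baseline to end of trial participation", and AEs leading to dose reduction, delay or permanent cessation.

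**The concern.** In a dose-escalation phase the natural question for an AE table is what happened at each dose. A column headed only by phase gives a percentage that belongs to no single dose. A reader of the report who wants the frequency or maximum grade at one level must rebuild it from the patient listings.

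This is a reporting matter. It does not touch oversight of dose decisions, which section 12.1 gives to the ISMC with access to all reported AEs, including those after the DLT window.

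**Working it through.** The plan gives no figure to reproduce on this point. The check compares the split named for each summary, then illustrates what pooling hides.

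**Step 1. Splits named in sections 10.3 and 10.4**

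| Output | Section | Split stated |
|---|---|---|
| DLT summary table | 10.3.1 | dose cohort |
| TEAE tables | 10.4.1.1 | trial phase |
| Biochemistry, hematology, coagulation | 10.4.1.2 | visit, cohort, trial phase |
| Urinalysis | 10.4.1.2 | none stated |
| Vital signs, physical examination, ECG, skin examination | 10.4.1.3 | visit, cohort, trial phase |
| ECOG PS, body weight, ADA | 10.4.1.3 | listed only |
| Best overall response | 10.4.2 | trial phase, dose cohort |

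Cohort is not named everywhere, but where the authors wanted it they added it to phase. The DLT table by SOC and "preferred term will be presented for each dose cohort, if applicable", and laboratory values are shown "using box plots by visits and by cohort and trial phase". One result is that skin examinations are split by dose while skin-toxicity AEs are not.

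**Step 2. Whether another table supplies AE rates by dose**

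The DLT table is by cohort, but section 9.5.2 limits it to the "observation period for DLTs, defined as Cycle 1, i.e. the initial 28 day period", and only events that meet the DLT criteria enter it. The endpoints in section 4.4.3.1 run to the end of trial participation and take in all grades. Later toxicity and toxicity below the DLT threshold therefore have no tabulated frequency by dose.

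**Step 3. What a pooled count hides**

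This step assumes cohort sizes but no event rates. It is an illustration and does not estimate bias.

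- Cohorts of 3 and 6, pooled count 3/9 = 33.3%. The possible splits (a of 3, b of 6, with a + b = 3) are:
  - 0/3 and 3/6: 0% and 50.0%
  - 1/3 and 2/6: 33.3% and 33.3%
  - 2/3 and 1/6: 66.7% and 16.7%
  - 3/3 and 0/6: 100% and 0%

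  That is 4 patterns.
- Three cohorts of 6 (18 patients, the top of the range in section 10.1), pooled count 6/18 = 33.3%. The number of triples (a, b, c), each from 0 to 6 and summing to 6, is C(8,2) = 28. They run from 2/6 at every dose to 0/6, 0/6 and 6/6.

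The phase-level table looks the same in every one of these cases.

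**Step 4. What cohort columns could show**

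With 0 events in n patients, the exact (Clopper-Pearson) 95% upper limit is 1 − 0.025^(1/n):

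- n = 3: 1 − 0.025^(1/3) = 70.8%
- n = 6: 1 − 0.025^(1/6) = 45.9%

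Cohort columns would therefore describe what was seen at each dose without establishing a dose effect.

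**The case against.** The strongest reply is that column layout is usually settled in the SAP and table shells, that the SAP is not at hand, and that nothing in the protocol forbids cohort columns. Under the same general rule in 10.4.1, sections 10.4.1.2 and 10.4.1.3 do split by cohort, so phase and cohort can coexist. Section 10.2 also has FAS patients contribute as allocated, which may be read as by allocated dose.

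Part of this stands: a SAP could add the columns. But the protocol does not leave the split open. It states one twice, and where section 10.4.1.1 does defer to the SAP, for the list of skin-toxicity terms, it says so. The as-allocated rule assigns patients to groups and does not set table columns.

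The second reply is that little follows from the omission. All AEs are listed, for roughly 9 to 18 escalation patients. The ISMC sees AEs as they arise. Section 10.4 places the secondary analyses after the expansion phase, so these tables were never going to inform the RP2D. Laboratory plots and skin examinations by cohort already show part of the expected toxicity. Amendment 3 ended enrollment and withdrew the objectives. All of this is correct and limits the importance of the point. It does not remove it: a listing is not a frequency table, gastrointestinal events have no by-cohort summary outside the DLT table, and sections 4.1 and 4.4 keep the clinical safety-related evaluations after Amendment 3.

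The third reply is that counting splits is true of any pooled count and treats unlikely patterns like likely ones. That is fair, and the counts are offered only to show what the table cannot distinguish.

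**Conclusion.** The point holds. As written, the escalation-phase TEAE tables pool patients over different Sym004 dose levels, while the same chapter splits most neighbouring outputs by cohort. The effect is confined to how AE frequencies and grades are reported by dose. Dose decisions are untouched and the raw information remains in the listings. Its importance is minor to moderate, and the text should be changed.

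The conclusion rests on a literal reading of sections 10.4.1 and 10.4.1.1 and on more than one dose level having been used in escalation. A SAP that already adds cohort columns would meet the point in practice, though the protocol wording would still differ from it.

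**What to change.** In sections 10.4.1 and 10.4.1.1, state that escalation-phase TEAE tables are presented by assigned Sym004 dose cohort plus a phase total, with any expansion-phase patients in a separate column. Using the assigned dose agrees with the as-allocated rule in section 10.2.

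The cost is extra columns built from data already collected. The drawback is small cells of about 3 to 6 patients, so the text should say that the cohort columns are descriptive, in keeping with section 10.4.1.

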10.4.1.2 Clinical Laboratory Values

Biochemistry, hematology and coagulation parameters will be presented using box plots by visits and by cohort and trial phase. In addition, individual patient biochemistry, hematology and coagulation parameters during the trial will be presented graphically using longitudinal plots. Urinalysis parameters will be summarized using descriptive statistics.

Laboratory values outside normal range by flagged and all laboratory values will be listed including CTCAE grading of abnormal values.

10.4.1.3 Other Assessments Related to Safety

Change in vital signs from baseline to end of trial participation will be summarized by visit, cohort and trial phase. Normal and abnormal findings in physical examination and ECG measurements will be presented in shift tables by visit, cohort and trial phase.

Skin examination will be summarized by visit, cohort and trial phase.

ECOG PS, body weight and ADA results will be listed.

10.4.2 Efficacy Endpoints and Analyses

The following anti-tumor response endpoints will be measured

- Documented OR (dose-escalation)
- Duration of OR from time of first PR or CR to PD
- Changes in sum of diameters of target lesions from baseline to end of trial participation

- SD for > 4 months
- Time to documented PD, death, patient withdrawal or end of trial participation, whichever comes first

All secondary efficacy endpoint will be presented using the FAS.

Best overall response by RECIST v1.1 will be summarized by trial phase and dose cohort by means of counts and percentages for the categories CR, PR, SD, PD and NE.

Number and percentages of patients with documented OR in the dose-escalation phase will be presented including corresponding 95% exact CI. All documented ORs (dose-escalation and dose-expansion phase) will be listed including duration of OR.

Duration of SD is calculated from baseline till first measurement of PD. The number and percentages of patients with SD for more than 4 months will be presented by trial phase.

Time to documented PD, death, patient withdrawal or end of trial participation, whichever comes first, will be presented using Kaplan-Meier plots by trial phase. The median survival time including 95% CI.

10.4.2.1 Other Efficacy Assessments

CEA will be assessed at Screening, at the end of every even cycle thereafter, and at EOT and 1MFU, if applicable. CEA will be presented using descriptive statistics.

10.4.3 Pharmacokinetic Endpoint and Analyses (Omitted as of Amendment 3)

The PK endpoints will be derived based on the concentration time curves of Sym004, mAb992 and mAb1024, respectively after the first and fourth infusion of Sym004 in the dose-escalation phase, regardless of delays in treatment. Refer to [Table 19](#).

Table 19 PK Endpoints Definitions and Derivations

Symbol	Definition and derivation
$AUC_{0-336h, sym004}$, $AUC_{0-336h, mAb992}$, $AUC_{0-336h, mAb1024}$	Area under the concentration-time curve from time zero (end of infusion) up to 336 hours. AUC_{0-336h} will be calculated using the linear trapezoidal method and interpolated in case of measurements after 336 hours, or extrapolated using terminal rate constant and the last quantifiable concentration, C_z
$AUC_{norm, 0-336h, sym004}$, $AUC_{norm, 0-336h, mAb992}$, $AUC_{norm, 0-336h, mAb1024}$	Dose normalized area under the concentration-time curve from time zero (end of infusion) up to 336 hours, calculated as AUC_{0-336h} divided by the dose infused
$\lambda_z, sym004$, $\lambda_z, mAb992$, $\lambda_z, mAb1024$	Terminal rate constant (negative of the slope of an ln-linear regression of the un-weighted data considering the terminal phase of the concentration-time curve \geq LOQ). λ_z is not an endpoint, but is used for derivation of endpoints

Symbol	Definition and derivation
$CL_{\text{sym004}}, CL_{\text{mAb992}}, CL_{\text{mAb1024}}$	Clearance (Dose/AUC _{0-336h})
$V_{Z_{\text{sym004}}}, V_{Z_{\text{mAb992}}}, V_{Z_{\text{mAb1024}}}$	Volume of distribution during the terminal phase (CL/ λ_z). Formula is used for both profiles as steady state is not reached.
$C_{\text{max, sym004}}, C_{\text{max, mAb992}}, C_{\text{max, mAb1024}}$	Maximum concentration
$C_{\text{trough, sym004}}, C_{\text{trough, mAb992}}, C_{\text{trough, mAb1024}}$	Concentration measured pre-infusion
$T_{\text{max, sym004}}, T_{\text{max, mAb992}}, T_{\text{max, mAb1024}}$	Time of maximum concentration
$T_{1/2, \text{sym004}}, T_{1/2, \text{mAb992}}, T_{1/2, \text{mAb1024}}$	Terminal half-life, calculated as $\ln(2)/\lambda_z$

C_{max} , C_{Trough} and T_{max} will be derived from observed data while AUC_{0-336h}, AUC_{norm, 0-336h}, CL, V_z , and $T_{1/2}$ will be estimated using non-compartmental methods and actual time points.

Individual curves of serum concentration versus time of Sym004, mAb992, and mAb1024, respectively will be presented on log- and linear scale for all patients who have received at least one infusion of Sym004, one plot for each profile after Sym004 administration (the first and fourth infusion) and one plot on linear scale for the whole period of time including trough serum concentrations only. In addition, mean concentration time curves will be presented on linear scale using nominal time point by cohort. Furthermore, the PK endpoints will be summarized by cohort and listed.

10.4.4 Pharmacodynamics Endpoints and Analyses (Omitted as of Amendment 3)

Potential biomarkers includes genes, gene transcripts and proteins of RTKs and molecules of the EGFR signaling pathway. All biomarkers will be listed.

Exploratory analysis using the biomarkers might be performed.

10.5 Interim Analysis

In the dose escalation phase clinical safety data will be assessed when the first patient in a 3-patient cohort has completed and tolerated Cycle 1, when 3 patients have completed and tolerated Cycle 1, and if the cohort is expanded when 6 patients have completed and tolerated Cycle 1.

An ISMC will be established to review all relevant safety and toxicity data of available patients. Please refer to [Section 12](#).

Based on an overall evaluation of the dose-escalation phase, a dose for the second phase of the trial will be recommended by the ISMC, i.e. the RP2D. The RP2D might not necessarily be either the MTD or the highest administered dose.

10.6 Data Collection and Analysis beyond Primary Analysis

As of Amendment 3: After the trial has closed enrollment and all DLT evaluation is completed, the Sponsor may reduce trial data collection to information needed for safety reporting required by the FDA and/or other regulatory authorities, as well as efficacy and safety follow-up data considered necessary by the Sponsor.

10.7 Deviations from the Statistical Plan

Any deviation(s) from the original analysis plan will be described in a CTP Amendment and/or in a SAP and/or in the final CTR, as appropriate.

11 ETHICS

11.1 Independent Ethics Committee or Institutional Review Board

An IEC/IRB will review the CTP and any amendments and advertisements used for recruitment, as well as the informed consent documents, their updates (if any), and any other written materials given to the patients. The CTR will include a list of all IECs/IRBs to which the CTP has been submitted and the name of the committee chair.

11.2 Patient Information and Informed Consent

The Investigator or his/her designee must obtain written informed consent from each patient before any trial related procedures are performed. Each patient must receive full patient information before giving consent. The patient information must contain full and adequate verbal and written information regarding the objective and procedures of the trial and the possible risks involved.

Before signing the informed consent form the patient must be given sufficient time to consider his/her possible participation. Each patient must also be informed about his/her right to withdraw from the trial at any time.

Each patient must sign the informed consent form; the patient receives a copy of the signed form and the original is retained in the Investigator Site File (ISF). The informed consent form must be signed and dated both by the patient and by the Investigator providing the information to the patient.

11.3 Compliance Reference Documents

The trial will be conducted in accordance with the CTP, the principles of the Declaration of Helsinki (18), ICH E6 GCP (1), and other laws in the countries where the trial takes place.

12 SAFETY SURVEILLANCE SET-UP

12.1 Independent Safety Monitoring Committee

An ISMC will be established for the trial. Functions and responsibilities of the ISMC are described in an ISMC charter.

Throughout dose-escalation, the ISMC will review all reported AEs and SAEs on an ongoing basis and will decide by consensus on the following:

- Agreement with the Investigator assessment of a medical event for a patient meeting the DLT definition
- Dose-escalation
- Dose-deescalation
- Dose level expansion (i.e. another 3 patients to be included on a given dose level)
- Suspension of enrollment
- Declaration of the MTD
- Declaration of the R2PD

NOTE: All reported AEs, including those occurring after the end of the DLT observation period, will be considered for decision-making by the ISMC.

Throughout the trial, the ISMC will monitor the overall safety of the trial and provide appropriate recommendations to the Sponsor regarding trial continuation, protocol modifications or trial suspension.

The conclusion of the ISMC meeting will be provided verbally to the Sponsor immediately after each meeting followed by signed written minutes within a few days.

Any safety related ISMC recommendation that may result in protocol changes will be reported to the HAs and IECs/IRBs. A letter of trial continuation after each ISMC meeting will be supplied to IECs/IRBs only if required.

